  - b. Mother's earliest delivery related claims date (year) from mother's claims records Infant birth year (from infant enrollment records). For mothers with delivery-related claims in December, infants with records in January of the following year will be included.
  - c. Infant's first enrollment date is not more than 180 days after mother's delivery related claims
- 2) Infants must be continuously enrolled for at least 90 days following birth which allows for the assessment of most major congenital birth defects

For comparator cohort A, we will include women who are exposed to other preventive medications during pregnancy as well as before LMP. When considering exposure to other preventive migraine medications before LMP, women will be included if exposure to these substances occurs within five of their half-lives prior to LMP.

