#### **9.2.2.2 Exclusion Criteria**

Women who are exposed to known teratogens (eg, valproate or topiramate) or other CGRP antagonists will be excluded if exposure to these substances occurs within five of their half-lives prior to LMP.

For comparator cohort B, women who have pharmacy claims for any preventive migraine medications will be excluded.

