### **9.3 Variables**

#### **9.3.1 Exposure Assessment**

Pregnant women who have pharmacy claims for erenumab-aooe (identified using NDC codes) in the 112 days prior to the LMP date (to allow for the half-life of erenumab) or during the pregnancy will be considered exposed to erenumab-aooe.

Exposure to erenumab-aooe will be categorized by dose (70 mg versus 140 mg), by length of exposure, and by timing in relation to trimester of pregnancy: before the last menstrual period (LMP, in the 112 days prior to the EDC, this is the exposure window of interest for major malformations), during the first trimester (from the LMP to 90 days after the LMP), during the second trimester (from day 91 after the LMP to day 180 after the LMP), and during the third trimester (from day 181 after the LMP to the end of pregnancy) (see [Section 9.3.1.1](#) for definitions of LMP).

For the comparator cohorts, comparator group A will include pregnant women with migraine who do not have pharmacy claims for erenumab-aooe in the 112 days prior to the LMP but do have evidence of the use of other preventive migraine medications. Comparator group B will include pregnant women with migraine who do not have pharmacy claims for erenumab-aooe or other anti-CGRP medications 112 days prior to the LMP date or during pregnancy

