### **9.6.2.5 Sensitivity Analysis**

#### **9.6.2.5.1 Subgroup Analysis**

Subgroups that will be explored if there is sufficient sample size include maternal age group at LMP (16-17 years, 18-40 years, 41-44 years), calendar year at LMP, comorbidities or medication use at baseline, concomitant medication use during pregnancy, dose of erenumab-aooe taken (70 or 140 mg), and patients who have migraine with aura or chronic migraine.

In addition to assessing outcomes in pregnant women exposed to erenumab-aooe before or during pregnancy and those not exposed to erenumab-aooe before or during pregnancy, we will also explore proportions of each of the outcomes in subgroups of the unexposed cohort, including migraine patients exposed to other CGRPs, migraine patients exposed to erenumab more than 112 days prior to the estimated date of conception and not during the pregnancy, migraine patients exposed to other preventive migraine medications, and migraine patients exposed to known teratogens in the one month prior to or during pregnancy. Also, outcomes will be described in migraine patients with claims for acute medication during the pregnancy.

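### Comparators A and B are defined inconsistently: Section 9.2.2 leaves women whose preventive exposure ended more than five half-lives before the LMP in neither group, and Section 9.3.1 says otherwise

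*Protocol*

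**What the plan says.** The protocol defines the two comparators in several places.

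- **Section 9.2.2.1, comparator A:** "For comparator cohort A, we will include women who are exposed to other preventive medications during pregnancy as well as before LMP". For the time before the LMP, "women will be included if exposure to these substances occurs within five of their half-lives prior to LMP".
- **Section 9.2.2.2, comparator B:** "For comparator cohort B, women who have pharmacy claims for any preventive migraine medications will be excluded". No window is given. The sentence just before it, on teratogens and other CGRP antagonists, does have one (five half-lives).
- **Section 9.3.1, comparator A:** women without an erenumab claim in the 112 days before the LMP "but do have evidence of the use of other preventive migraine medications". No window is given for the other preventive.
- **Section 9.3.1, comparator B:** women "who do not have pharmacy claims for erenumab-aooe or other anti-CGRP medications 112 days prior to the LMP date or during pregnancy". Other preventives are not mentioned.
- **Section 8.1, primary objective:** B is unexposed to erenumab or other preventives before or during pregnancy, with no length for the period before.
- **Section 9.6.2.4.1, primary analysis:** A was exposed immediately before or during pregnancy; B was unexposed to any preventive, again with no window.

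Section 9.3.3 lists acute and preventive migraine treatments in the baseline period as covariates. Section 9.2.4 sets that period at 365 days before the LMP. Section 9.6.2.4.1 takes the propensity-score covariates from Section 9.3.3 and makes formal comparison conditional on adequate overlap.

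**The concern.** These passages decide who enters the two comparators of the primary objective. Two programmers working from Section 9.2.2 and from Section 9.3.1 would build different cohorts.

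Three things are at stake. Former users of a preventive have no settled place. Under Section 9.3.1 even a woman who takes an oral preventive during pregnancy meets the wording for B, contrary to Section 8.1. And under the literal rule of Section 9.2.2.2, B contains nobody with past preventive use, so a variable that the plan intends to adjust for has no variation in B. That undermines the overlap condition on which the erenumab-versus-B comparison depends.

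**Working it through.** The plan gives no figure for this point, so the passages are set side by side first.

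**1. Where each woman falls.** Take women with migraine and no erenumab or anti-CGRP claim, whose other preventive is not itself an excluded teratogen. Section 9.2.2.1 is read as use in pregnancy or before the LMP, as in Section 8.1.

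| Use of another preventive | Section 9.2.2 | Section 9.3.1 |
|---|---|---|
| During pregnancy | A | wording of A and of B |
| Last exposure within five half-lives before LMP | A | wording of A and of B |
| Last exposure earlier than that | neither | wording of A and of B |
| None | B | B |

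Sections 8.1 and 9.6.2.4.1 do not settle the third row, because neither gives a length for the time before pregnancy. Section 8.1 does contradict B membership in the first row.

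**2. Length of the gap under Section 9.2.2.** A's pre-LMP window in days is w = 5 × half-life in hours / 24. The unassigned part of a look-back of L days is L − w. The half-lives are assumptions, because the protocol gives none.

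| Assumed half-life | w (days) | 112 − w | 365 − w |
|---|---|---|---|
| 4 h | 0.8 | 111.2 | 364.2 |
| 48 h | 10 | 102 | 355 |
| 168 h | 35 | 77 | 330 |

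These rows count from the last exposure. If exposure runs to the end of the days supplied, the unassigned fill dates within 112 days shrink:
- 30-day fill: 112 − (30 + 0.8) = 81.2 down to 112 − (30 + 10) = 72 days.
- 90-day fill: 112 − (90 + 0.8) = 21.2 down to 112 − (90 + 10) = 12 days.

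**3. Effect on balance with B.** Let q be the share of erenumab women with a baseline claim for another preventive (not given). Under the literal rule the share in B is 0.

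Before weighting, the standardized mean difference is SMD = q / √(q(1 − q)/2) = √(2q/(1 − q)). The Abstract takes SMD < 0.10 as good balance. Solving 2q/(1 − q) < 0.01 gives q < 0.01/2.01 = 0.5%.

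For weighting, consider this covariate alone with four B women per erenumab woman (Section 9.2.3). An erenumab woman with past use has propensity score 1 and weight 1, and no B woman stands opposite her. The weights carry the erenumab group to the size of the whole sample, five times its own, so its weighted share of past users is q/5. B's share stays 0 under any weights. With weighted standard deviations, SMD = √(2x/(1 − x)) with x = q/5.

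| q | SMD before | SMD after |
|---|---|---|
| 10% | √(0.2/0.9) = 0.47 | √(0.04/0.98) = 0.20 |
| 25% | √(0.5/0.75) = 0.82 | √(0.1/0.95) = 0.32 |

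The limit of 0.10 is passed once q exceeds 5 × 0.5% = 2.5%. With unweighted standard deviations, the weighted SMD is √(2q/(1 − q))/5, and the limit is q = 0.25/2.25 = 11%. Even when the SMD passes, erenumab women with past use still have no counterpart in B.

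**The case against.** The case on the other side has real substance.

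- **The text does not fix B as never-treated.** A reader might infer that B bars a preventive claim at any time in a woman's history. Section 9.2.2.2 is silent on time, and Section 8.1 speaks of exposure before or during pregnancy. The look-back is unstated, and a statistical analysis plan could state it. This stands, but that plan would still have to override one of two conflicting protocol sections.
- **Some women who stopped are in a comparator.** A reader might infer that no comparator contains women who stopped a preventive before conceiving. That is wrong: those who stopped within five half-lives are in A, and Section 9.3.1 would admit earlier stoppers.
- **The erenumab window follows the same idea.** Women with a claim "in the 112 days prior to the LMP date (to allow for the half-life of erenumab) or during the pregnancy will be considered exposed", so both windows rest on half-life. A woman many half-lives past an oral preventive corresponds to one who stopped erenumab more than 112 days before the LMP, who is not in the exposed cohort either. The difference is one of calendar length, and it does not show a built-in bias against erenumab.
- **Section 9.6.2.5.1 is not a clear contradiction.** It places "migraine patients exposed to erenumab more than 112 days prior to the estimated date of conception and not during the pregnancy" in the unexposed cohort, but that cohort also includes users of other CGRP drugs, other preventives and teratogens. It is broader than B.
- **Timing analyses exist.** Section 9.6.2.5.3 separates erenumab exposure during pregnancy from exposure before it. That does not place former users of other preventives.
- **An untreated B beside a treated A is a defensible pair.** This is true, but it does not fit a propensity model that includes past preventive use.

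**Conclusion.** The point holds as an inconsistency in the definitions of A and B, with one consequence for the analysis. Under Section 9.2.2 read literally, women whose preventive exposure ended more than five half-lives before the LMP are in neither comparator. Under Section 9.3.1 they, and users of an oral preventive during pregnancy, meet the wording for B. The literal B rule also removes overlap with B for every erenumab woman with past preventive use, and weighting cannot restore it.

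The size in days rests on assumed half-lives, and the balance thresholds on a one-covariate illustration. The number of women affected cannot be derived, because the documents give no count of former users in any cohort. For the same reason, no percentage bias in the malformation comparison can be stated, nor that B has milder disease. The passages should be reconciled before the cohorts are built.

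**What to change.** 1. Reconcile Sections 8.1, 9.2.2.1, 9.2.2.2, 9.3.1 and 9.6.2.4.1 so that each comparator has one definition, used throughout.
2. Give B's exclusion an explicit window aligned with A's inclusion window: preventive exposure within that pre-LMP window or during pregnancy. Former users are then eligible for B.
3. In Section 9.3.1, add other preventives to the exclusions for B. Also state that A has no erenumab claim during pregnancy, as the Study Design Schema does. The present text bars erenumab from A only before the LMP, so changing B's window alone would not make the cohorts exclusive.
4. Adjust for past preventive use in the comparison with B, and report B without former users as a sensitivity analysis.

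The cost is protocol wording and some cohort programming. Measured against the literal Section 9.2.2.2, the pool for B can only grow. The downside is that the main B is no longer a never-treated group; the sensitivity analysis keeps that contrast available.

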## 7. Rationale and Background

### 7.1 Diseases and Therapeutic Area

Migraine is a neurological disorder characterized by recurrent headache attacks of moderate to severe pain. Migraines affect up to 18% of the female population and 6% of the male population; the prevalence peaks in middle life (30 to 49 years) (7.9%-9.0% in men and 25.5%-28.1% in women) and is lower in children/adolescents and those older than age 60 (Lipton et al, 2007).

Treatment for migraine includes medications for acute migraine as well as preventive medications. Acute treatments that are commonly used for migraine attacks include triptans, ergots, nonsteroidal anti-inflammatory drugs (NSAIDs), acetaminophen, and antiemetic agents (Charles 2017). The most commonly used therapies for migraine prevention include tricyclic antidepressants, beta-blockers, anticonvulsants (eg, topiramate and divalproex sodium), and botulinum toxin (Charles 2017).

Migraine often improves during pregnancy; however, this varies depending on whether women have migraine with aura. For patients who have migraine without aura, approximately 47% of women will have improvement or remission of migraine in the first trimester, increasing to 83% in the second trimester, and 87% in the third trimester (Sances et al, 2003). Migraine with aura is less likely to improve during pregnancy (Robbins 2018).

Up to 70% of pregnant women with migraine require a behavioral or a pharmacologic intervention (Contag et al, 2009). Although nonpharmacologic therapies are recommended for migraine management during pregnancy, acute medications used to treat migraine include acetaminophen and metoclopramide; however, narcotics, NSAIDs (depending on the trimester) and triptans may also be used (Robbins 2018). Triptans

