## **8. Research Question and Objectives**

### **8.1 Primary**

The primary objective is to estimate and compare the proportion of live-born infants with major congenital malformations among (1) women with migraine directly exposed to erenumab-aooe prior to and during pregnancy, (2) women with migraine exposed to other preventive migraine medications prior to or during pregnancy (comparator group A), and (3) women with migraine not exposed to erenumab-aooe or other preventive migraine medications prior to or during pregnancy (comparator group B). Comparative analyses will be undertaken if there is sufficient sample size and adequate distribution of covariates to adjust for confounding.

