### 9.3.3 Covariate Assessment

Study cohorts will be described according to baseline covariates. Demographic attributes will be determined on the cohort entry date while others will be assessed during the baseline period, unless otherwise specified. All covariate information will be ascertained through inpatient and/or outpatient claims for diagnoses and procedures, and through pharmacy claims utilizing ICD-10 CM for diagnoses; ICD-10 PCS, CPT, or HCPCS codes for procedures; and GPI or NDC codes for dispensings. Additional details will be provided in the Statistical Analysis Plan (SAP) and the Medical Record Plan (MRP).

Covariates to be assessed include the following:

- Maternal age at estimated LMP (in years)

- Maternal race, if available

- Calendar year at estimated LMP

- Geographic region of health plan

- Migraine characteristics (eg, migraine with aura, chronic migraine)

- Comorbid conditions at baseline (eg, chronic hypertension, hyperlipidemia, diabetes, polycystic ovarian syndrome, hypothyroidism, hyperthyroidism, depression, anxiety, epilepsy), identified through ICD-10-CM diagnosis codes

- Medications in the baseline period (eg, acute and preventive migraine treatments, other treatments not for migraine, suspected teratogenic medications), identified through NDC codes or HCPCS codes

- Adverse events during pregnancy (eg, pre-eclampsia, gestational diabetes), identified through ICD-10-CM diagnosis codes

- Concomitant medications with claims after or a days supply that overlaps the LMP date and by trimester during the pregnancy (eg, acute migraine treatments, other treatments not for migraine, suspected teratogenic medications), identified through NDC codes or HCPCS codes

- History of obstetric outcomes (eg, prior pregnancies, multiple gestation, outcomes of prior pregnancies including spontaneous abortions) using all available history

- Use of prenatal testing

- Resource utilization (eg, number of prenatal visits, types of providers visited, emergency department visits)

- Body mass index, if available

- Alcohol, tobacco, and substance abuse, if available

Exposure to infections during pregnancy, if available  
 Previous history of congenital malformations, if available

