#### 9.6.2.4 Analysis of the Primary, Secondary, and Exploratory Endpoint(s)

##### 9.6.2.4.1 Analysis of the Primary Endpoint

Frequencies and the proportions (95% CIs) of major congenital malformations, in infants born to the following three cohorts of women with migraine, will be estimated: (1) those exposed to erenumab-aooe immediately prior to or during pregnancy, (2) those exposed to other preventive migraine medications immediately prior to or during pregnancy, and (3) those unexposed to any migraine preventive medications, including erenumab-aooe.

If there is sufficient sample size and adequate overlap in the distribution of confounding variables, formal comparisons to estimate odds ratios and corresponding 95% CIs will be undertaken. We will use inverse probability of treatment weights to address confounding. We will fit a logistic regression model for the conditional probability of treatment,  $Pr(A_i = a|L_i)$ , where  $L_i$  is a vector of measured baseline confounders of the exposure and the outcome. The conditional probability of treatment given a set of covariates is commonly referred to as the propensity score (PS), and a histogram of the overlap in the propensity score will be presented. IP of treatment weights will be constructed as:

$$\widehat{W}_i^2 = \frac{1}{\widehat{Pr}(A_i = a|L_i)}$$

For the analyses described here,  $L_i$  will be based on subject-matter knowledge (see covariates identified in [Section 9.3.3](#)).

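### Group B's exclusion looks only at pharmacy claims, so a woman whose preventive was given and billed by a provider can be counted as unexposed, and can also meet the group A rule

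*Protocol*

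**What the plan says.** The intent is clear. The primary objective (Protocol 8.1) describes "women with migraine not exposed to erenumab-aooe or other preventive migraine medications prior to or during pregnancy (comparator group B"), and the primary analysis (9.6.2.4.1) calls the same women "those unexposed to any migraine preventive medications, including erenumab-aooe".

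The operational rules are as follows.

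- 9.2.2.2, group B: "women who have pharmacy claims for any preventive migraine medications will be excluded". It gives no window and no other claim type.
- 9.3.1, group B: women "who do not have pharmacy claims for erenumab-aooe or other anti-CGRP medications 112 days prior to the LMP date or during pregnancy". This again relies on pharmacy claims, and it names only erenumab and its class.
- 9.3.1, group A: no erenumab claim before the LMP, "but do have evidence of the use of other preventive migraine medications". No claim type is given.
- 9.2.2.2, all women: exposure to other CGRP antagonists within five half-lives before the LMP is an exclusion, with no claim type named.

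Section 7.1 counts "anticonvulsants (eg, topiramate and divalproex sodium), and botulinum toxin" among the commonly used preventives. Section 9.3.3 takes a wider source for the baseline covariate: "Medications in the baseline period (eg, acute and preventive migraine treatments, other treatments not for migraine, suspected teratogenic medications), identified through NDC codes or HCPCS". Section 9.2.2.1 likewise uses NDC or HCPCS codes to find acute migraine drugs for eligibility.

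**The concern.** Section 9.4 describes a pharmacy claim as something the pharmacy submits when a prescription is filled. A drug injected in a clinic and billed by the provider is a medical claim, so the 9.2.2.2 rule does not see it. A programmer who follows the text would keep that woman in the unexposed cohort, while the covariate table built under 9.3.3 could show her as a preventive user. Because group A asks only for evidence of use, she could be eligible for both comparators.

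At stake is the meaning of the group B comparison. It is the only contrast of erenumab with no preventive treatment, and it should not contain treated women because of where their drug was billed.

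**Working it through.** **Step 1. Set the rules side by side.**

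| Use | Section | Source of drug information |
|---|---|---|
| Group B, intended | 8.1, 9.6.2.4.1 | any preventive, no source limit |
| Group B, exclusion of preventives | 9.2.2.2 | pharmacy claims |
| Group B, erenumab and anti-CGRP | 9.3.1 | pharmacy claims |
| Group A, inclusion | 9.3.1 | evidence of use, source open |
| Other CGRP antagonists before LMP | 9.2.2.2 | exposure, source open |
| Baseline preventive treatment | 9.3.3 | NDC or HCPCS codes |

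Take a woman with botulinum toxin in early pregnancy, billed only as a medical claim. She has no pharmacy claim, so 9.2.2.2 does not exclude her from B. She has no erenumab or anti-CGRP claim, so 9.3.1 does not either. She has evidence of using another preventive, so she meets the group A wording. The two comparators are therefore not mutually exclusive as written. Had her drug been dispensed through a pharmacy, the exclusion would have worked. She can enter B; she does not necessarily do so.

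**Step 2. Anti-CGRP drugs.** Exposure before the LMP is already covered by the general exclusion in 9.2.2.2, whatever the claim type. What remains is exposure during pregnancy, where the only group B rule aimed at this class is "pharmacy claims for erenumab-aooe or other anti-CGRP medications 112 days prior to the LMP date or during pregnancy".

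**Step 3. Reproduce the plan's figure for scale.** Inputs from 9.5 and Table 2: background risk 3%, relative risk 2.00 (so 6% in the exposed), 1:4 allocation, 80% power. Two-sided alpha 0.05 is assumed because the protocol states none. With k = 4 and pooled risk (0.06 + 4 × 0.03)/5 = 0.036:

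n = [1.96 × √(1.25 × 0.036 × 0.964) + 0.8416 × √(0.06 × 0.94 + 0.03 × 0.97/4)]² / 0.03²
= [0.4082 + 0.2124]² / 0.0009 ≈ 428.

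Table 2 gives 425, so the figure is reproduced. Power at 425 is 79.8%.

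**Step 4. How much could contamination matter?** Let f be the share of group B that is in fact treated and k′ the risk in those women relative to the truly unexposed. The risk in B is then 0.03 × (1 − f + f·k′), and the observed relative risk is 0.06 divided by that. The protocol gives neither f nor k′; both are assumptions. The nearest figure is the estimate in 9.5 that about 0.9% of pregnant women with migraine take a preventive during pregnancy. Clinic-billed use is only part of that. Group B's intended window also reaches back before pregnancy, so 0.9% is a benchmark and not a ceiling. The 5% and 10% rows are stress values.

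| f | k′ = 0.5 | k′ = 1 | k′ = 1.5 | k′ = 2 |
|---|---|---|---|---|
| 0.9% | 2.01 | 2.00 | 1.99 | 1.98 |
| 5% | 2.05 | 2.00 | 1.95 | 1.90 |
| 10% | 2.11 | 2.00 | 1.90 | 1.82 |

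For example, f = 0.9% and k′ = 2 give 0.03 × 1.009 = 0.03027, and 0.06/0.03027 = 1.98, with power 79.0% at 425 exposed. The extreme cell (10%, doubled risk) gives 1.82 and power 70.3%. These are unweighted.

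**The case against.** The best counter-argument is that 9.4 lists a HCPCS code alongside the NDC among its pharmacy claims fields, so the term might be wider than it looks. That makes the text less clear-cut, but the list still describes claims that pharmacies submit, and nothing in 9.2.2.2 extends the exclusion to medical claims.

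A second argument is that the intent in 8.1 and 9.6.2.4.1 is plain and that code lists belong in the SAP. Code lists do. Here, however, the protocol itself fixes the data source, and an SAP that follows it inherits the mismatch.

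Third, 9.8.1.1 discloses gaps in drug capture, and 9.6.2.5.3 plans to explore quantitative bias analysis for exposure misclassification. The disclosed gaps are over-the-counter drugs, inpatient dispensing and samples, not drugs a provider has billed. A bias analysis is also a poor substitute for reading claims already held.

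What does stand is the objection on size. A reader might infer that these women resemble erenumab users, receive large inverse probability weights and so dominate group B. The protocol gives no basis for any weight ratio, nor does it say that users of clinic-administered preventives have the most severe migraine; comparisons are also conditional on adequate overlap. A reader might likewise infer that an anti-CGRP class effect is being hidden. The pre-LMP exclusion in 9.2.2.2 covers other CGRP antagonists without limiting claim type, and the protocol does not say that any such product is provider-billed. Neither inference is supported.

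**Conclusion.** The point holds as a mismatch between group B's objective and the rule that implements it: women treated with a provider-billed preventive can enter the unexposed group, and the wording lets the same woman qualify for group A. For anti-CGRP drugs this is limited to exposure during pregnancy.

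No figure in the protocol changes. Bias could go either way and vanishes if these women have the background risk. At the 0.9% benchmark with an assumed doubled risk, a relative risk of 2.00 is read as about 1.98. The conclusion rests on one fact from outside the protocol, that botulinum toxin is often billed by the provider and not dispensed by a pharmacy. Low-to-moderate priority, worth correcting because it is cheap.

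**What to change.** In 9.2.2.2 and in the comparator definitions of 9.3.1, identify other preventive and anti-CGRP medications from pharmacy or medical claims (NDC, HCPCS or CPT codes), in line with 9.3.3. Use a single code list to assign groups A and B, and state that a woman who meets the group A rule cannot be in group B. State the window over which the group B exclusion applies, so that 9.2.2.2, 9.3.1 and 9.6.2.4.1 agree.

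The cost is a wording change, a few added codes and slightly fewer women in group B. Section 9.4 shows that medical claims with CPT and HCPCS codes are already held in both databases, so no new data are needed.
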